10.3.4.1. Adverse Events

AEs are classified based on the Medical Dictionary for Regulatory Activities (MedDRA). A TEAE is defined as an event that first occurred or worsened in severity after the first dose of study treatment and on or prior to the date of the last visit within the treatment period. Both the date/time of the event and the date/time of the dose (ie, injection) are considered when determining TEAEs. For each TEAE, the severity is recorded according to the patient's or physician's perceived severity of the event (mild, moderate, or severe). A follow-up emergent adverse event (FEAE) is defined as an event that first occurred or worsened in severity after the date of Week 52 (Visit 11) or the ETV. For events that are sex-specific, the denominator and computation of the percentage will only include subjects from the given sex.

An overall summary of AEs will be provided for Period 2, including the number and percentage of subjects who experienced TEAEs, TEAEs by maximum severity, death, SAEs, TEAEs related to study drug, discontinuations from treatment due to an AE, and treatment-emergent adverse events of special interest. TEAEs (all, by maximum severity, and TEAEs possibly related to study drug by the investigator), SAEs including deaths, and AEs that lead to treatment discontinuation will be summarized and analyzed by MedDRA system organ class (SOC) and preferred term.

In addition to general safety parameters, safety information on specific topics of adverse events of special interest will also be presented. Potential adverse events of special interest will be identified by a standardized MedDRA query (SMQ) or a Lilly-defined MedDRA preferred term listing.

Follow-Up emergent AEs, SAEs including deaths, and AEs that lead to study discontinuation will be summarized by MedDRA system organ class and preferred term for Period 3.

10.3.4.2. Clinical Laboratory Tests

Laboratory assessments will be analyzed as mean changes from baseline and as incidence of treatment-emergent abnormal, high, or low laboratory values (see below). Shift tables will be presented for selected parameters.

- For categorical laboratory tests:
 - Treatment-emergent **abnormal** value = a change from normal at all baseline visits to abnormal at any time postbaseline.
- For continuous laboratory tests:

- Treatment-emergent **high** value = a change from a value less than or equal to the high limit at all baseline visits to a value greater than the high limit at any time postbaseline.
- Treatment-emergent low value = a change from a value greater than or equal to the low limit at all baseline visits to a value less than the low limit at any time postbaseline.

10.3.4.3. Vital Signs, Physical Findings, and Other Safety Evaluations

Vital signs will be analyzed as mean changes from baseline and as incidence of abnormal values and will be summarized for both predose and postdose at Week 0 (Week 2) and Week 52 (Visit 11), as applicable.

Suicide-related thoughts and behaviors and self-injurious behavior with no suicidal intent, based on the C-SSRS, will be listed by patient.

10.3.5. Pharmacokinetic/Pharmacodynamic Analyses

Not applicable.

10.3.6. Other Analyses

10.3.6.1. Subgroup Analyses

Subgroup analysis will be conducted using the ITT population.

Subgroups to be evaluated will include concomitant csDMARD use at baseline (Yes vs No), concomitant MTX use at baseline (Yes vs No), sex (male vs female), age group (<65 vs ≥65). A detailed description of the subgroup variables will be provided in the SAP.

A logistic regression model with treatment, subgroup, and the interaction of subgroup by treatment included as factors will be used. The subgroup-by-treatment interaction will be tested at the significance level of 0.10. Treatment group differences will be evaluated within each category of the subgroup using Fisher's exact test, regardless of whether the interaction is statistically significant. Missing data will be imputed using NRI. If any group within the subgroup is less than 10% of the total population, only summaries of the efficacy data will be provided (ie, no inferential testing will be performed).

10.3.7. Interim Analyses

An interim database lock will occur, and the analysis will be performed at the time (that is, a cutoff date) when the last patient completes Visit 8 (Week 24), completes ETV, or discontinues from Period 2. This database lock will include all data collected by the cutoff date including data after Week 24 from the Open-Label Treatment Period (Period 2) and follow-up data from patients who have begun Post-Treatment Follow-Up Period (Period 3).

This interim database lock at Week 24 will be considered the primary database lock for this study because all primary and major secondary study objectives will be assessed at this time. Since the primary time point of interest is Week 24, efficacy and health outcomes data will be

reported up to Week 24 because of the lack of complete data for all patients beyond this visit. However, all safety data collected up to the cutoff date will be reported.

A final database lock will occur after all enrolled patients have completed or discontinued the Post-Treatment Follow-Up Period (Period 3). After the final database lock, all efficacy, health outcomes, and safety data collected until study completion will be reported.

There will be no data monitoring committee.

11. References

- Amjevita [package insert]. Thousand Oaks, CA: Amgen Inc; 2016.
- Antoni C, Krueger GG, de Vlam K, Birbara C, Beutler A, Guzzo C, Zhou B, Dooley LT, Kavanaugh A. IMPACT 2 Investigators. Infliximab improves signs and symptoms of psoriatic arthritis: results of the IMPACT 2 trial. *Ann Rheum Dis.* 2005a;64(8):1150–1157.
- Antoni CE, Kavanaugh A, Kirkham B Tutuncu Z, Burmester GR, Schneider U, Furst DE, Molitor J, Keystone E, Gladman D, Manger B, Wassenberg S, Weier R, Wallace DJ, Weisman MH, Kalden JR, Smolen J. Sustained benefits of infliximab therapy for dermatologic and articular manifestations of psoriatic arthritis: results from the Infliximab Multinational Psoriatic Arthritis Controlled Trial (IMPACT). *Arthritis Rheum*. 2005b;52(4):1227-1236.

Appendix 1. Abbreviations and Definitions

Term	Definition
ACR	American College of Rheumatology
ACR Core Set	Consists of 7 disease activity measurements: tender joint count, swollen joint count, patient's assessment of pain, Patient's Global Assessment of Disease Activity, Physician's Global Assessment of Disease Activity, Patient's Assessment of Physical Function, and an acute-phase reactant value.
ACR Responder	ACR20 Responder
. Terrasoponav	A patient who has at least 20% improvement in both tender and swollen joint counts and at least 20% improvement in a minimum of 3 of the following 5 criteria: patient's assessment of arthritis pain, Patient's Global Assessment of Disease Activity, Physician's Global Assessment of Disease Activity, Patient's Assessment of Physical Function (Health Assessment Questionnaire-Disability Index), and an acute-phase reactant value (CRP or ESR). ACR50 Responder
	-
	A patient who has at least 50% improvement in both tender and swollen joint counts and at least 50% improvement in a minimum of 3 of the following 5 criteria: patient's assessment of arthritis pain, Patient's Global Assessment of Disease Activity, Physician's Global Assessment of Disease Activity, Patient's Assessment of Physical Function (Health Assessment Questionnaire-Disability Index), and an acute-phase reactant value (CRP or ESR). ACR70 Responder
	=
	A patient who has at least 70% improvement in both tender and swollen joint counts and at least 70% improvement in a minimum of 3 of the following 5 criteria: patient's assessment of arthritis pain, Patient's Global Assessment of Disease Activity, Physician's Global Assessment of Disease Activity, Patient's Assessment of Physical Function (Health Assessment Questionnaire-Disability Index), and an acute-phase reactant value (CRP or ESR).
AE	adverse event: Any untoward medical occurrence in a patient or clinical investigation subject administered a pharmaceutical product that does not necessarily have a causal relationship with this treatment. An adverse event can therefore be any unfavorable and unintended sign (including an abnormal laboratory finding), symptom, or disease temporally associated with the use of a medicinal (investigational) product, whether or not related to the medicinal (investigational) product.
ALP	alkaline phosphatase
ALT	alanine aminotransferase
AST	aspartate aminotransferase
audit	A systematic and independent examination of the trial-related activities and documents to determine whether the evaluated trial-related activities were conducted, and the data were recorded, analyzed, and accurately reported according to the protocol, applicable standard operating procedures, good clinical practice (GCP), and the applicable regulatory requirement(s).
BCG	Bacillus Calmette-Guérin
bDMARD	Biologic disease-modifying anti-rheumatic drug (see also DMARD); examples of biologics include—but are not limited to—etanercept (Enbrel®), adalimumab (Humira®), and infliximab (Remicade®)

blinding A procedure in which one or more parties to the trial are kept unaware of the treatment

assignment(s). A single-blind study is one in which the investigator and/or his staff are aware of the treatment but the patient is not, or vice versa, or when the sponsor is aware of the treatment but the investigator and/his staff and the patient are not. A double-blind study is one in which neither the patient nor any of the investigator or sponsor staff who are involved in the treatment or clinical evaluation of the subjects are aware

of the treatment received.

BSA body surface area; measured in 1% increments with area of patient's hand including

palm, fingers and thumb = 1%

CASPAR Classification for Psoriatic Arthritis

CEC Clinical Events Committee; responsible for adjudicating cerebrocardiovascular AEs to

achieve consistency in reporting

CI confidence interval

clinical research Individual responsible for the medical conduct of the study. Responsibilities of the physician CRP may be performed by a physician, clinical research scientist, global safety

physician or other medical officer.

complaint A complaint is any written, electronic, or oral communication that alleges deficiencies

related to the identity, quality, purity, durability, reliability, safety or effectiveness, or

performance of a drug or drug delivery system.

compliance Adherence to all the trial-related requirements, good clinical practice (GCP)

requirements, and the applicable regulatory requirements.

confirmation A process used to confirm that laboratory test results meet the quality requirements

defined by the laboratory generating the data and that Lilly is confident that results are accurate. Confirmation will either occur immediately after initial testing or will require that samples be held to be retested at some defined time point, depending on the steps

required to obtain confirmed results.

consent The act of obtaining informed consent for participation in a clinical trial from patients

deemed eligible or potentially eligible to participate in the clinical trial. Patients entered into a trial are those who sign the informed consent form directly or through

their legally acceptable representatives.

CRP C-reactive protein
CSR clinical study report

C-SSRS Columbia—Suicide Severity Rating Scale

DAS28-CRP Disease Activity Score (28 diarthrodial joint count) based on C-reactive protein

DLQI Dermatology Life Quality Index

DNA deoxyribonucleic acid

eCRF Case report form (electronic case report form). Sometimes referred to as clinical report

form. A printed or electronic form for recording study participants' data during a

clinical study, as required by the protocol.

efficacy Efficacy is the ability of a treatment to achieve a beneficial intended result.

end of study (trial) End of study (trial) is the date of the last visit or last scheduled procedure shown in the

Study Schedule for the last active subject in the study.

enroll The act of assigning a patient to a treatment. Patients who are enrolled in the trial are

those who have been assigned to a treatment.

enter Patients entered into a trial are those who sign the informed consent form directly or

through their legally acceptable representatives.

enthesitis Inflammation of tendons and ligaments that can manifest as localized pain and

tenderness.

EQ-5D-5L European Quality of Life–5 Dimensions 5 Level

ERB Ethical Review Board; a board or committee (institutional, regional, or national)

composed of medical and nonmedical members whose responsibility is to verify that

the safety, welfare, and human rights of the patients participating in a clinical study are

protected.

ETV Early Termination Visit

EU European Union

FSH follicle-stimulating hormone GCP good clinical practice

HAQ-DI Health Assessment Questionnaire-Disability Index

HBcAb+ positive for anti-hepatitis B core antibody
HBsAb+ positive for anti-hepatitis B surface antibody
HBsAg+ positive for hepatitis B surface antigen

HBV hepatitis B virus HCV hepatitis C virus

HIV human immunodeficiency virus

HIVAb human immunodeficiency virus antibody hs-CRP high sensitivity (assay) C-reactive protein

IB Investigator's Brochure
IBD inflammatory bowel disease
ICF informed consent form

ICH International Conference on Harmonisation

IL Interleukin (eg, IL-17; a proinflammatory cytokine produced by Th17 cells)

informed consent A process by which a patient voluntarily confirms his or her willingness to participate

in a particular trial, after having been informed of all aspects of the trial that are relevant to the patient's decision to participate. Informed consent is documented by means of a

written, signed, and dated informed consent form.

interim analysis An interim analysis is an analysis of clinical study data, separated into treatment groups,

that is conducted before the final reporting database is created/locked.

investigational product A pharmaceutical form of an active ingredient or placebo being tested or used as a

reference in a clinical trial, including products already on the market when used or assembled (formulated or packaged) in a way different from the authorized form, or marketed products used for an unauthorized indication, or marketed products used to

gain further information about the authorized form.

investigator A person responsible for the conduct of the clinical study at a study site. If a study is

conducted by a team of individuals at a study site, the investigator is the responsible

leader of the team and may be called the principal investigator.

ITT intention to treat; the principle that asserts that the effect of a treatment policy can be

best assessed by evaluating on the basis of the intention to treat a patient (that is, the planned treatment regimen) rather than the actual treatment given. It has the consequence that patients allocated to a treatment group should be followed up,

assessed, and analyzed as members of that group irrespective of their compliance to the

planned course of treatment.

ERB Ethical Review Board; a board or committee (institutional, regional, or national)

composed of medical and nonmedical members whose responsibility is to verify that the safety, welfare, and human rights of the patients participating in a clinical study are

protected.

IV intravenous

IWRS interactive web-response system LDI-B Leeds Dactylitis Index—Basic

legal representative An individual, judicial, or other body authorized under applicable law to consent on

behalf of a prospective patient, to the patient's participation in the clinical study.

LEI Leeds Enthesitis Index

LOCF last observation carried forward MDA Minimal Disease Activity

MedDRA Medical Dictionary for Regulatory Activities

MI myocardial infarction

MMRM mixed-effects model repeated measures

Modified CPDAI Modified Composite Psoriatic Disease Activity Index

MTX methotrexate

NAPSI Fingernails Nail Psoriasis Severity Index Fingernails

NRI nonresponder imputation NRS numeric rating scale

PASI Psoriasis Area and Severity Index

patient A study participant who has the disease or condition for which the investigational

product is targeted.

PPD purified protein derivative

Ps psoriasis

PsA psoriatic arthritis

PsARC Psoriatic Arthritic Response Criteria

QoL quality of life Q2W every 2 weeks Q4W every 4 weeks RA rheumatoid arthritis

randomize Refers to a method of treatment assignment. The point of randomization in this trial is

the point at which treatment is assigned and the patient begins treatment; thus, patients

who are randomized in the trial are those who have been assigned to a treatment.

registration The act of assigning a registration number to the subject indicating that the registration

center/sponsor/principal investigator or subinvestigator has verified that the subject

meets the inclusion criteria and none of the exclusion criteria.

rescreen To screen a patient who was previously declared a screen failure for the same study.

SAE serious adverse event SAP statistical analysis plan

SC subcutaneous

screen The act of determining if an individual meets minimum requirements to become part of

a pool of potential candidates for participation in a clinical study.

SF-36 Medical Outcomes Study 36-Item Short Form Health Survey

SJC swollen joint count

sPGA static Physician Global Assessment of psoriasis SUSAR suspected unexpected serious adverse reaction

TB tuberculosis
TBL total bilirubin level

TEAE Treatment-emergent adverse event; an untoward medical occurrence that emerges

during a defined treatment period, having been absent pretreatment, or worsens relative

to the pretreatment state, which and does not necessarily have to have a causal

relationship with this treatment.

TJC tender joint count
TNF tumor necrosis factor
UC ulcerative colitis

ULN	upper limit of normal
VAS	visual analog scale

Appendix 2. Clinical Laboratory Tests

Assays to be performed by the central laboratory unless otherwise noted.

Clinical Laboratory Tests

Hematology
Hemoglobin
Clinical Chemistry
Serum Concentrations of:

Hematocrit Sodium
Erythrocyte count (RBC) Potassium
Mean cell volume Total bilirubin
Mean cell hemoglobin concentration Direct bilirubin
Leukocytes (WBC) Alkaline phosphatase

Platelets Alanine aminotransferase (ALT)

Absolute counts of: Aspartate aminotransferase (AST)

Neutrophils, segmented Triglycerides
Lymphocytes Total cholesterol
Monocytes HDL/LDL cholesterol

Eosinophils GGT

Basophils Proteins (total)

Blood urea nitrogen (BUN)

Other Tests Creatinine
Human immunodeficiency virus antibody (HIV) Uric acid
Hangetitis P. Surface anticon (HISA a)

Hepatitis B Surface antigen (HBsAg)

Calcium

Anti-Hepatitis B Surface antibody (HBsAb) Glucose, fasting at Visit 2 but nonfasting throughout

Anti-Hepatitis B Core antibody (HBcAb) study, if clinically indicated

Anti-Hepatitis C antibody Albumin

Purified Protein Derivative (PPD)^a Creatine Phosphokinase (CPK)

QuantiFERON®-TB Gold^a hs-CRP

T-SPOT.TB^a HBV DNA HCV RNA

Rheumatoid factor (RF)

Urinalysis Pregnancy Test (females only)

Specific gravity Serum
pH Urine^b
Protein FSH

Glucose Ketones Blood

Urine leukocyte esterase

Abbreviations: FSH = follicle-stimulating hormone; GGT = gamma-glutamyl transferase; HDL = high-density lipoprotein; HIVab = human immunodeficiency virus antibody; LDL = low-density lipoprotein; RBC = red blood cells; WBC = white blood cells.

- a Test may be done by the physician, nurse, or at the local laboratory.
- b Assay to be performed by study site or self-administered by patient. Additional urine pregnancy testing can be performed at the investigator's discretion. If required per local regulations, testing can occur at other intervals during the study treatment period and/or follow-up period.

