Habits (tobacco, alcohol use)		X						
Concomitant medications	X	X	X	X	X	X	X	X
Review adverse events	X	X	X	X	X	X	X	X
Randomization		X						
Administer Study Drug			I	Sec	e Table RH	CF.2.1 ^e	I.	I
Dispense Study Drug and Study Drug Administration Log		X		X	X	X	X	X
Collect/Review/Enter Data from Study Drug Administration Log		X		X	X	X	X	X
Clinical Efficacy								
Patient-Rated Assessments							_	
Patient's Assessment of		X		X	X	X	X	X
Pain VAS		Λ		Λ	Λ	Λ	Λ	Λ
Patient's Global								
Assessment of Disease		X		X	X	X	X	X
Activity VAS								
HAQ-DI		X		X	X	X	X	X
Itch NRS		X		X	X	X	X	X
SF-36		X		X		X	X	X

	Screen-	Treatment Phase: Study Drug Administration													
	ing Period 1	Baseline		Ope	n-Label Tı	reatment P	eriod 2 ^a								
Visit No (V)	V1	V2	V3 ^b	V4	V5	V6	V7	V8							
Study Week (W)		W0	W1	W4	W8	W12	W16	W24							
Study Days	-28d	0d	7 ± 2d	28 ± 2d	56 ± 2d	84 ± 4d	112 ± 4d	168 ± 4d							
EQ-5D-5L		X		X		X	X	X							
Fatigue Severity NRS		X		X		X	X	X							
DLQI		X		X	X	X	X	X							
Clinician-Rated or Admini	istered Ass	sessments	•	•	•	•		•							
TJC/SJC (68/66 joints)	X	X		X	X	X	X	X							
Physician's Global Assessment of Disease		X		X	X	X	X	X							
Activity VAS	+	X		v	V	X	v	v							
PASI	v	!		X	X		X	X							
% Body Surface Area Enthesitis Assessment	X	X		X	X	X	X	X							
(SPARCC and LEI)															
LDI-B		X				X	X	X							
sPGA		X													
NAPSI Fingernails		X				X	X	X							
C-SSRS	X	X		X	X	X	X	X							
Self-Harm Supplement Form and Self-Harm Follow-Up Form	X	X		X	X	X	X	X							
Treatment Satisfaction Questionnaire						X		X							
Laboratory Tests															
Administer TB test ^f	X														
Chest x-ray	X ^g														
ECG		X^h													
FSH	Xi														
HIV/HCV	X														
HBV Panel ^j	X														
HBV DNA ^k	X	X				X		X							
Serum pregnancy test ¹	X														
Urine pregnancy test ^m		X				X		X							
Serum chemistry	X	X ⁿ		X		X		X							
Hematology	X	X		X		X		X							
Urinalysis	X	X						X							
RF	X														
hs-CRP		X		X	X	X	X	X							

Study Schedule, Protocol I1F-MC-RHCF

Study Schedule, Protocol IIF-MC-RHCF	Treatmen	t Phase: Stud	dy Drug Admi	nistration
	Op	en-Label Tre	atment Period	l 2 ^a
Visit No (V)	V9	V10	V11	ETV
Study Week (W)	W32	W40	W52	
Study Days	$224 \pm 4d$	$280 \pm 4d$	$364 \pm 4d$	
Physical examination ^c			X	X
Weight			X	X
Sitting blood pressure and pulse	X	X	X	X
Concomitant medications	X	X	X	X
Review adverse events	X	X	X	X
Administer Study Drug		See Table	RHCF.2.1 ^e	

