- f In countries where the QuantiFERON®-TB Gold test or T-SPOT® is available, either test may be used instead of the purified PPD TB test. The QuantiFERON®-TB Gold test may be performed locally or centrally; the T-SPOT® must be performed locally. PPD tests must be read 48 to 72 hours after Visit 1. See Section 9.4.4.2 for TB testing details.

Study Schedule, Protocol I1F-MC-RHCF

- A chest x-ray (posterior-anterior view) will be taken at screening (Visit 1) and assessed locally, unless one has been obtained within the past 6 months and the x-ray or results are available for review.
- h Obtain ECG within 1 week of Visit 2 (prior to the first dose); assessed locally.
- i For female patients ≥40 and <60 years of age who have had a cessation of menses for at least 12 months, a follicle-stimulating hormone (FSH) test will be performed to confirm nonchildbearing potential (FSH ≥ 40 mIU/mL).
- j All patients will be tested for HBV.
- ^k Patients who meet criteria for HBV monitoring (see Section 9.4.5.4) will be identified by the central laboratory at baseline and monitored according to the study schedule.
- 1 Only for females of childbearing potential.
- ^m Only for females of childbearing potential. Additional urine pregnancy testing can be performed at the investigator's discretion or per applicable regulations/guidance.
- ⁿ Visit 2 should be a fasting visit.
- o Patients receiving study drug who discontinue at any time prior to the end of the study or who complete the study (Week 52) will enter the Post-Treatment Follow-Up Period occurring from last treatment visit or ETV up to a minimum of 12 weeks after that visit. Visit 803 will only occur if a patient's neutrophil counts have not returned to the criteria defined in Sections 5.1.3 and 8.1.1.

 Table RHCF.2.1.
 Study Drug Administration Schedule

Visit	2	3			4				5				6				7								8
Weeks	0 ^a	1	2	3	4	5	6	7	8	9	10	11	12	13	14	15	16	17	18	19	20	21	22	23	24
Ixekizumab 80 mg Q2W/Q4W Moderate-to-Severe Plaque Ps ^b	X (160 mg)		X		X		X		X		X		X				X				X				X
Ixekizumab 80 mg Q4W ^c	X (160 mg)				X				X				X				X				X				X
Adalimumab 40 mg Q2W ^d	X (40 mg)		X		X		X		X		X		X		X		X		X		X		X		X
Adalimumab 40 mg Q2W Moderate-to-Severe Plaque Ps ^e	X (80 mg)	X		X		X		X		X		X		X		X		X		X		X		X	

Visit								9								10												11
Weeks	25	26	27	28	29	30	31	32	33	34	35	36	37	38	39	40	41	42	43	44	45	46	47	48	49	50	51	52
Ixekizumab 80 mg Q2W/Q4W Moderate-to-Severe Plaque Ps ^b				X				X				X				X				X				X				

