6.15. Safety Analyses

The primary safety analyses will focus on comparisons of ixekizumab versus adalimumab in the Open-Label Treatment Period (Period 2). Fisher's exact test will be used for all AEs and other categorical safety data. Continuous vital sign and laboratory values will be analyzed by an ANCOVA with treatment and baseline value in the model. Type 3 sums of squares will be used. The significance of within-treatment group changes from baseline will be evaluated by testing whether the treatment group LSMeans changes from baseline are different from zero using a t-statistic. In addition to the LSMeans and tests, the standard deviation, minimum, median, and maximum will be displayed. Unless otherwise specified, change from baseline will include only those subjects with both baseline and post-baseline measures.

For safety analyses, p-values should be interpreted with caution as the analyses are intended to be descriptive and should not be thought of as hypothesis testing, unless there is a prespecified hypothesis. P-values and CIs, if reported, provide some evidence of the strength of the finding and are only useful as a flagging mechanism.

Summaries of safety data collected during the Post-Treatment Follow-Up Period will be presented separately. The categorical safety measures will be summarized with incidence rates. The continuous safety measures will be summarized using mean changes.

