6.15.4. Clinical Laboratory Evaluation

Laboratory evaluations will be summarized and analyzed for the following periods:

- Open-Label Treatment Period (Safety Population)
- Post-Treatment Follow-Up Period (Post-Treatment Follow-Up Population)

Laboratory analyses will include planned analytes only. Planned analytes are those specified in the protocol. However, unplanned/unscheduled measurements of planned analytes will be included/ excluded as specified in the relevant sections. Examples of unplanned/unscheduled measurements include those that the clinical investigator orders as a repeat test or “retest” of a laboratory test if he or she has received an abnormal value, and those the investigator orders for a “follow-up visit” due to clinical concerns.

Laboratory test observed values at each visit (starting at baseline) and change from baseline to each visit will be displayed in box plots (with outliers displayed) for patients who have both a baseline and at least 1 post-baseline result for Period 2 and Period 3, respectively. Baseline will be the last nonmissing observation in the baseline period. Original-scale data will be used for the display. Unscheduled visits and repeat measurements will be excluded. In each of the plots displaying values at each visit, lines indicating the performing lab reference ranges will be added. Displays using both standard (SI) and conventional (CN) units will be provided (when different). The following summary statistics will be included in a table below the box plot: N, mean, standard deviation, minimum, Q1, median, Q3, and maximum. P-values and confidence limits will not be included in the summary statistics at the bottom of the box plot. Box plots will be used to evaluate trends over time and to assess a potential impact of outliers on central tendency summaries.

The number and percentages of patients with treatment-emergent abnormal, high, or low laboratory results at any time will be summarized by treatment for the treatment period. Scheduled visits, unscheduled visits, and repeat measurements will be included. Performing lab reference ranges will be used to define the low and high limits.

- Categorical laboratory tests:
 - A treatment-emergent **abnormal** result is defined as a change from normal at all baseline visits to abnormal at any time during the treatment period.
- Numerical laboratory tests:

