 - A treatment-emergent **high** result is defined as a change from a value less than or equal to the high limit at all baseline visits to a value greater than the high limit at any time during the treatment period.
 - A treatment-emergent **low** result is defined as a change from a value greater than or equal to the low limit at all baseline visits to a value less than the low limit at any time during the treatment period.

Alanine aminotransferase (ALT), aspartate aminotransferase (AST), total bilirubin, alkaline phosphatase (ALP), neutrophils, leukocytes, platelets, and lymphocytes will not be included in this treatment-emergent abnormal, high, or low laboratory results analysis. A separate analysis

to address the risk of liver injury is described in [Table RHCF.6.7](#) in which performing lab reference ranges will be used.

By-patient listing of abnormal laboratory test results (criteria defined in the shift tables excluding the normal category) for parameters of special interest (hepatic, leukocytes, and platelets) will be provided.

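### Glucose and triglycerides have a fasting baseline and later draws not required to be fasting, so within-arm change tests and absolute treatment-emergent-high percentages mix feeding state with treatment

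*Protocol*

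**What the plan says.** **Sampling.** In Protocol Section 2 (Schedule of Activities), "Serum chemistry" is drawn at Visits 1 and 2, at Weeks 4, 12, 24, 40 and 52, and at early termination. Only the Visit 2 cell carries footnote n: "Visit 2 should be a fasting visit". The glucose entry in Protocol Appendix 2 reads "Glucose, fasting at Visit 2 but nonfasting throughout" and runs on to "study, if clinically indicated". Triglycerides are in the same chemistry list with no fasting instruction of their own.

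**Baseline.** SAP 6.1.1 uses the last value on or before the first injection and expects this to be Visit 2 in most cases. SAP 6.15.4 says of the laboratory box plots: "Baseline will be the last nonmissing observation in the baseline period".

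**Analyses.**
- SAP 6.15 fits an ANCOVA with treatment and baseline to laboratory values. It assesses within-group change by "testing whether the treatment group LSMeans changes from baseline are different from zero using a t-statistic".
- SAP 6.15.4 plots change from baseline by visit to look for trends over time.
- SAP 6.15.4 defines a treatment-emergent high as a move from at or below the limit "at all baseline visits to a value greater than the high limit at any time during the treatment period", using the performing laboratory's ranges.
- The analytes removed from that count are ALT, AST, total bilirubin, ALP, neutrophils, leukocytes, platelets and lymphocytes. Glucose and triglycerides stay in.

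Neither document provides a fasting flag, a matched baseline or a caveat for these two analytes.

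**The concern.** The required sampling condition changes at the same point as treatment starts. If nonfasting glucose and triglycerides run higher than fasting ones, both will appear to rise on treatment even when neither drug has any effect.

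The ixekizumab-adalimumab difference is protected because both arms share the switch. However, that contrast cannot show whether both drugs raise glucose or lipids. With no placebo arm, a reader asking that question would turn to the within-arm changes, the box-plot trends and the absolute treatment-emergent-high percentages. Those are the outputs in which feeding state and treatment cannot be separated.

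**Working it through.** The plan states no figure on this point, so there is none to reproduce. The check asks how often the planned outputs would signal a change when there is no drug effect.

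**Inputs from the documents.** 275 patients per arm (Protocol 10.1); 72% expected to complete Week 52 (Protocol 5.2), so 0.72 × 275 = 198 per arm; two-sided alpha 0.05 (SAP 6.1); chemistry at Weeks 4, 12, 24, 40 and 52.

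**Assumptions not in the documents.** Nonfasting values exceed fasting ones; the size of the shift; the within-patient correlation (0.5 or 0.7); the percentile at which the upper limit sits; and that draws without a fasting instruction, including Visit 1, are nonfasting.

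**1. Within-arm test.** With a shift of d standard deviations of the change, the probability of a significant rise is approximately Φ(d√n − 1.96).

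| d | n = 275 (√n = 16.58) | n = 198 (√n = 14.07) |
|---|---|---|
| 0.1 | Φ(−0.30) = 38% | Φ(−0.55) = 29% |
| 0.2 | Φ(1.36) = 91% | Φ(0.85) = 80% |
| 0.3 | Φ(3.02) = 99.9% | Φ(2.26) = 99% |

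A simulation of the SAP ANCOVA, taking Week 24 as the example visit (two identical arms of 275, 600 trials per scenario), agrees. With matched feeding state the within-arm test rejects in about 5-7% of trials. With a shift of 0.2 SD of a single value it rejects in 96-99.5%. That shift is 0.20 SD of the change at correlation 0.5, since √(2 × 0.5) = 1. At correlation 0.7 it is 0.26 SD, since √(2 × 0.3) = 0.77.

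**2. Between-arm test.** In the same simulation the ANCOVA treatment contrast rejects in about 4-8% of trials, with or without the shift. The common shift cancels.

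**3. Treatment-emergent high.** The SAP rule was applied with both Visit 1 and Visit 2 required to be at or below the limit, Visit 1 nonfasting, and five post-baseline draws. Entries are the percentage of eligible patients; shifts are in SDs of a single value; ranges cover the two correlations.

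| Shift | Limit at 97.5th fasting percentile | Limit at 90th fasting percentile |
|---|---|---|
| none (matched) | 5.0-7.2% | 14.3-21.3% |
| 0.2 | 7.5-10.9% | 19.9-28.4% |
| 0.5 | 12.9-18.1% | 28.9-40.2% |
| 0.8 | 20.1-27.8% | 39.2-52.3% |

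If only Visit 2 counted as baseline, the 97.5th-percentile column would read 5.9-8.0% matched, then 9.2-12.3%, 16.6-21.0% and 26.6-32.8%. Requiring Visit 1 to be normal as well reduces the inflation but does not remove it in any scenario.

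**The case against.** The strongest reply is that little depends on these outputs. SAP 6.15 centres the primary safety analysis on ixekizumab versus adalimumab, which is unbiased. It also calls safety p-values descriptive and useful only for flagging. Glucose and lipids are neither adverse events of special interest nor special safety topics, and the box plots carry no p-values. All of this stands, and it limits the point to descriptive within-arm summaries. It does not remove the point, because a flag that can be set off by feeding state alone does not serve even a flagging purpose.

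Two further objections also stand as limits:
- The ending of the Appendix 2 glucose entry may make later glucose conditional. There would then not be a full scheduled series at 275 per arm, and the rejection probabilities for glucose would be lower. Any later nonfasting value would still be compared with a fasting baseline.
- Nonfasting is written only for glucose. For triglycerides it is inferred from the shared panel and the Visit-2-only footnote.

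A reader might infer that most patients would be counted as treatment-emergent high. The documents do not support that. The rule covers all baseline visits, which appears to bring in the Visit 1 draw, and the limits are laboratory ranges that neither document gives. A reader might also infer that Visit 1 is a ready-made nonfasting baseline. The protocol gives Visit 1 no fasting instruction, so its feeding state is simply not controlled.

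**Conclusion.** The point holds for glucose and triglycerides, in three outputs: the within-arm tests of change, the box-plot trends, and the absolute treatment-emergent-high percentages. As planned, these mix feeding state with treatment, and nothing in either document corrects or labels that.

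The size is conditional, because the shift is assumed rather than documented. With no drug effect, a shift of 0.2 SD of the change is enough to make the within-arm test significant about 91% of the time at 275 per arm, or 80% at 198. With the limit at the 97.5th percentile and Visit 1 nonfasting, treatment-emergent-high incidence is about 7.5-28% for shifts of 0.2 to 0.8 SD, against 5-7% matched.

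It would go too far to conclude that the report will show a significant metabolic rise on both drugs, since that depends on a shift found nowhere in the documents. Nor does the point touch the between-arm safety comparison or any efficacy result. It is a cheap improvement to the safety tables.

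**What to change.** In SAP 6.15.4, add for glucose and triglycerides:
- a statement that the Visit 2 baseline is fasting and that later draws are not required to be;
- no within-group tests of change from Visit 2;
- treatment-emergent-high counts reported only as between-group comparisons, with a footnote on sampling state;
- the same footnote on the change-from-baseline box plots;
- the between-group ANCOVA kept as planned.

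In Protocol Appendix 2, clarify what the closing phrase "study, if clinically indicated" makes conditional: the later glucose test itself, or its fasting state.

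Do not substitute Visit 1 as the baseline. Its fasting state is not controlled, it can fall up to 28 days before the first dose, and using it would depart from the baseline definition in SAP 6.1.1.

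The cost is a few lines of text and the loss of two descriptive within-arm outputs. SAP 6.15.4 already treats some analytes separately, so the change fits its structure.
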